2.1 Objectives & Hypotheses

1.0 Amendment 1 – Dated May 14, 2020

1. Imipenem-relebactam changed to imipenem-cilastatin-relebactam throughout the protocol to document inclusion of cilastatin. This maintains consistency with the package insert for the drug and also clarifies the dosage.
2. The dosage has been changed to 1.25 grams throughout the protocol. This total dose is consistent with the package insert and contains 500mg of imipenem, 500mg of cilastatin, and 250mg of relebactam. Note, the total amount of imipenem and relebactam administered to the patient is not different from the original protocol.
3. Section 2.1: correct misspelling
4. Section 2.2: Background updated to indicate approval of imipenem-cilastatin-relebactam for complicated urinary tract and intra-abdominal infections.
5. Section 2.5 modified to indicate collection of blood in K2EDTA lavender tubes instead of sodium heparin tubes. The assay to be used requires K2EDTA tubes for collection. As a result, the maximum blood volume per sample has been reduced from 7 mL to 4 mL, since the latter is the maximum volume of a lavender top tube. Additional details provided on processing of plasma with MES stabilizer.
6. Section 2.5 modified to add free drug assessments of imipenem and relebactam.
7. Section 2.7 modified to provide details of analytical service by Q2 Solutions, Ithaca NY.
8. Section 2.7 modified to incorporate fraction unbound estimates into Monte Carlo simulations.

1.1 Amendment 2 – Dated July 31, 2020

1. Section 2.5 modified to indicate collection of additional pre-dose blood sample within 30 minutes of infusion start time.

1.2 Amendment 3 – Dated December 22, 2020

1. Section 2.5 inclusion criteria #3 modified to lower creatinine clearance (CrCL) from 150 mL/min to 130 mL/min. This has been changed throughout protocol accordingly. This will increase the target population while still limiting patients to those with augmented renal clearance.
2. Section 2.5 inclusion criteria #4 modified to include only antibiotic use as a method for determining whether or not a patient has a documented or presumed infection, and removing other criteria related to infection (temperature, elevated WBC).
3. Section 2.5 inclusion criteria #10 modified to reduce minimum APACHE II score from >12 to ≥10. The threshold of 12 was arbitrary, while the intent is to include relatively sick patients in the study, which will still be the case.
4. Section 2.5 exclusion criteria #9 modified to remove valproic acid.
5. Section 2.5 addition of criteria #10 excluding patients currently receiving or anticipated to receive valproic acid. The change in criteria 9 and 10 will allow for patients to receive imipenem-cilastatin-relebactam despite a prior recent history of valproic acid use.

2.1 Objectives

1. Determine the single-dose pharmacokinetics of intravenous imipenem (when administered as imipenem-cilastatin-relebactam 1.25 grams as a 30 minute infusion) in adult critically ill patients with known or suspected sepsis and ARC
2. Determine the single-dose pharmacokinetics of intravenous relebactam (when administered as imipenem-cilastatin-relebactam 1.25 grams as a 30 minute infusion) in adult critically ill patients with known or suspected sepsis and ARC
3. Determine a dose of imipenem-cilastatin-relebactam that achieves greater than 90% probability of pharmacodynamic target attainment using the imipenem *P. aeruginosa* susceptibility breakpoint of 2 µg/mL and the MIC distribution of a contemporary *P. aeruginosa* and KPC producing *K. pneumoniae* population
4. Assess the safety and tolerability of single-dose imipenem-cilastatin-relebactam in adult critically ill patients with known or suspected sepsis and ARC

2.1.1 Null Hypotheses

The pharmacokinetics of imipenem and relebactam will not be affected by the presence of augmented renal clearance in adult critically ill patients.

2.2 Background & Rationale, Significance of Selected Topic & Preliminary Data

The continuous rise of bacterial resistance to antibiotics is among the most challenging concerns in contemporary clinical medicine. Imipenem-relebactam (Merck&Co, Inc., Kenilworth, NJ) is an investigational broad-spectrum antibiotic that combines the known carbapenem, imipenem, with the novel beta-lactamase inhibitor, relebactam (1). The addition of relebactam provides imipenem protection against serine based carbapenemases, including the *Klebsiella pneumoniae* carbapenemase (KPC), as well as improved activity against imipenem non-susceptible *Pseudomonas aeruginosa* (2). Imipenem-cilastatin-relebactam is approved in the United States for complicated urinary tract infections and complicated intra-abdominal infections; it is under investigation for hospital-acquired and ventilator-associated pneumonia, and specifically for multidrug resistant Gram-negative infections when it retains activity (1).

Given its potent activity against KPC producing Enterobacteriaceae and imipenem non-susceptible *P. aeruginosa*, it is reasonable to consider that imipenem-cilastatin-relebactam will be used in patients who are critically ill in the intensive care unit (ICU). Critically ill patients may have varied kidney dysfunction as a result of acute infection. Most clinicians are familiar with acute and chronic kidney impairment, which results in decreased elimination of drugs that are cleared by glomerular filtration. Both imipenem and relebactam are predominantly excreted via the kidneys (3); therefore, dosage adjustments will be required based on calculated creatinine clearance. Sepsis in ICU patients, however, may also produce a syndrome called Augmented Renal Clearance (ARC), whereby increased blood flow to the kidneys results in enhanced renal elimination and solute clearance (4). This enhanced clearance is typically defined by an 8 hour urine creatinine clearance $\geq 130 \text{ ml/min/1.73 m}^2$ and has been observed in as many as 65% of ICU patients on at least one day during their ICU admission (4,5). ARC has been directly linked to sub-therapeutic concentrations of β -lactam antibiotics, including imipenem (6,7,8,9). Furthermore, simulation of another carbapenem, meropenem, based on pharmacokinetics observed in patients with ARC resulted in regrowth of a susceptible *Pseudomonas aeruginosa* in hollow-fiber experiments (10).

	
To our knowledge, the pharmacokinetics of relebactam, with or without imipenem, have not been studied in critically ill patients with ARC. If ARC affects relebactam clearance to a similar degree as imipenem and other renally eliminated β-lactams, larger doses or prolonged infusion may be required to maintain optimized pharmacodynamic exposure. Importantly, the effect of ARC on beta-lactam exposure is highly dependent on the MIC of the causative organism. Therefore, it is also possible that the lower MICs observed with imipenem when combined with relebactam may mean that ARC has little effect on achievable time above the MIC exposure.

2.3 Study Design
	
This will be a single center, observational, pharmacokinetic study. Eligible patients will be evaluated for inclusion/exclusion criteria. Following consent by the patient, legal authorized representative (LAR), or next of kin, participants will receive a single dose of imipenem-cilastatin-relebactam 1.25 grams administered as a 30 minute infusion. Blood samples will be collected over the following 6 hours (consistent with proposed dosing interval) for characterization of imipenem and relebactam concentrations. Pharmacokinetic analyses will be conducted to describe parameter estimates in patients with ARC. We aim to enroll up to 12 patients so that complete data for 8 patients with ARC can be collected.

2.4 Study Flowchart
	
N/A


2.5 Study Procedures
	
Study Locations The Center for Anti-Infective Research and Development (CAIRD), Hartford Hospital, CT will coordinate the study. The study will be conducted in the medical, surgical, and neurosurgical ICUs at Hartford Hospital, an 890 bed tertiary care hospital in Hartford, CT. Institutional Review Board approval will be required based on local regulations. If LAR or next of kin are consented, local regulations will be followed to collect written informed consent from the patient once able to provide consent.
 
Study Population Inclusion Criteria Patients eligible to participate in the study must meet all of the following criteria prior to any study-related procedure:
 
 1. Male or female aged 18-54 years; 2. APACHE II score ≥ 10 and ≤ 35; 3. Creatinine clearance (CrCL) ≥ 130 mL/min (as calculated by the Cockcroft-Gault equation using ideal or adjusted body weight) within 24 hours of dosing (Note: using a higher CrCL threshold for Cockcroft-Gault CrCL will increase likelihood that enrolled participants have a urine CrCL ≥ 130 ml/min/1.73 m² and thus qualify as ARC); 4. Documented infection or presumed infection by receiving another antibiotic. 
Exclusion Criteria Patients will be considered ineligible if they meet any of the following criteria:
 
 1. If female, currently pregnant or breast feeding; 2. History of any moderate or severe hypersensitivity or allergic reaction to any β-lactam antibiotic (Note: mild rash or erythema to penicillin or cephalosporin antibiotics would not disqualify a patient if they have received a carbapenem without problem); 3. History of chronic kidney disease, hemodialysis, or peritoneal dialysis; or history of acute renal replacement therapy (e.g., hemodialysis,

hemofiltration, hemodiafiltration) or extracorporeal membrane oxygenation (ECMO) associated with current illness;

4. Suspected rhabdomyolysis or creatine kinase > 10,000 U/L;
5. Any serum creatinine (SCr) before dosing that is increased ≥ 0.3 mg/dL from the baseline SCr used qualifying for enrollment;
6. Urinary output <20 ml/hour for at least 2 hours (oliguria) within 24 hours before enrollment;
7. Sustained (at least 1 hour) hypotension (systolic pressure < 90 mmHG or mean arterial pressure < 55 mmHg) refractory to vasopressors or IV fluid resuscitation for at least 24 hours before enrollment;
8. Significant anemia defined as a hemoglobin < 8 g/dL at baseline;
9. Use of probenecid or imipenem within 3 days before study drug infusion;
10. Current use of valproic acid or anticipated use during study enrollment.
11. Acute liver injury, defined as aspartate aminotransferase (AST) or alanine aminotransferase (ALT) > 5 times the upper limit of normal, or AST or ALT > 3 times the upper limit of normal with an associated total bilirubin > 2 times upper limit of normal;
12. Any rapidly-progressing disease or immediately life-threatening illness (defined as imminent death within 48 hours in the opinion of the investigator);
13. Any condition or circumstance that, in the opinion of the investigator, would compromise the safety of the patient or the quality of study data;
14. Planned or prior participation in any other interventional drug study within 30 days.

Study Procedures

Screening/Baseline

Screening/Baseline assessments and procedures must be completed within 24 hours before the start of the study drug infusion. Potential subjects who do not meet enrollment criteria may, as appropriate, repeat the screening assessments once at a later time for possible enrollment into the study. Local laboratory results will be used to determine subject eligibility for study enrollment. Any protocol-required eligibility laboratory evaluations already done as part of the patient's regular medical care within 24 hours before the start of the study drug infusion on Study Day 1 do not have to be repeated for purposes of determining eligibility for this study.

- Obtain informed consent in writing from patient, legal authorized representative, or next of kin, according to local regulations.
- Clinical Assessments:
 - Obtain a complete medical and surgical history, including: a) all active conditions and all conditions diagnosed within the previous 1 year
 - Perform a complete physical examination (general/appearance; head, eyes, ears, nose, and throat [HEENT]; neurological; pulmonary; cardiovascular; gastrointestinal; musculoskeletal; and skin)
 - Record height and weight
 - Record resting pulse, blood pressure, and respiratory rate; oxygen saturation (by pulse oximeter), including rate of supplemental oxygen (i.e., FiO₂); ventilator support; and highest (or lowest if hypothermia) daily temperature (oral, rectal, tympanic, or core) measured
 - Record total fluid balance including total fluid intake and total fluid output for the period encompassing the signing of the ICF to the start of the study drug infusion
 - Record each component of the Acute Physiology and Chronic Health Evaluation II (APACHE II) assessment at Screening/Baseline

- Record all prior medications taken or received within 3 days before study drug infusion
- Identify, assess, and record any new adverse events or Serious Adverse Events (SAE) after signing of informed consent
- Laboratory Assessments:
 - Collect the following labs within 24 hours of study dose administration: serum creatinine, blood urea nitrogen, glucose, sodium, potassium, chloride, bicarbonate, albumin, total protein, complete blood count (CBC) with differential, total bilirubin, direct bilirubin, alkaline phosphate, alanine aminotransferase, aspartame aminotransferase, and urine analysis with microscopy. A serum hCG test will be collected for females of child-bearing potential.
- Calculation of CrCL using Cockcroft-Gault based on screening/baseline serum creatinine:

$$\text{Calculated CrCL} = \frac{(140 - \text{age in years}) \times \text{ideal body weight (kg)}^{a,b,c}}{72 \times \text{SCr (mg/dL)}}$$

Multiply by 0.85 for female patients

^a Ideal body weight (IBW, kg): Males = 50 + [2.3 × (Height (in) - 60)];
Females = 45.5 + [2.3 × (Height (in) - 60)]

^b For patients with total body weight (TBW) that is greater than 20% over IBW, use adjusted body weight (ABW, kg): IBW + 0.4*(TBW-IBW)

^c If TBW is less than IBW, use TBW in equation

Study Medication Administration

All participants will receive a single dose of imipenem-cilastatin-relebactam 1.25 grams as a 30 minute (+/- 5 minutes) infusion. Imipenem-cilastatin-relebactam vials will be supplied by the study sponsor. The dose will be prepared according to manufacturer recommendations in precisely 100 ml of 0.9% sodium chloride. Imipenem-cilastatin-relebactam must be administered through a peripheral intravenous catheter, peripherally inserted central catheter (PICC), central line, or port-a-catheter, whichever is determined to be most appropriate by the local investigator and care provider for each participant. Participants will also receive standard intravenous antibiotic therapy (excluding generic or branded intravenous imipenem) to treat their suspected infection, as determined by the responsible provider. No other intravenous medications will be co-administered with imipenem-cilastatin-relebactam.

Study Day 1

- Within 8 hours of beginning study medication infusion, a pre-dose SCr will be collected to confirm calculated CrCL remains ≥130 mL/min and that no change in SCr was observed to be ≥ 0.3 mg/dL from the baseline SCr used qualifying for enrollment.
- An 8 hour (± 1 hour) urine creatinine collection will be initiated within 4 hours prior to study medication infusion. The results of the measured urine CrCL will be used to confirm ARC in the patient over the time period that blood samples for imipenem-cilastatin-relebactam are collected.

$$\text{Measured CrCL (ml/min)} = \frac{\text{UCr (mg/dL)} \times \text{urine volume (mL)}}{\text{Predose-SCr} \times \text{time}^a}$$

Abbreviations: CrCl = creatinine clearance; SCr = serum creatinine; UCr = urine creatinine.

^a Time = The 8-hour urine collection has a ± 1 hour window (i.e., 480 min \pm 60 min); use the exact number of minutes of the urine collection in the equation

- Vital signs (temperature, heart rate, blood pressure, respiratory rate) will be recorded within 15 minutes prior to starting the study drug infusion.
- Participants will receive the single dose of imipenem-relebactam as described above. Exact start and stop times will be recorded in military time.
- Identify, assess, and record any new adverse events or Serious Adverse Events (SAE)
- Concomitant medications will be recorded.
- Blood Sample Collection: Seven blood samples (4 ml per sample) will be collected in K2EDTA vacutainers at the following time points to determine the concentrations of imipenem and relebactam in plasma: 0 hour (within 30 minutes prior to the start of infusion), 0.5 hours (end of infusion), 0.75, 1, 2, 4, and 6 hours after the start of the infusion. The timing of all blood samples should be \pm 5 minutes of protocol defined time, except for the 0.5 hour (peak concentration), which can be + 5 minutes and should be collected as close to the end of the infusion as possible. All blood samples will be collected via a peripheral intravenous catheter inserted into the contralateral arm to drug administration for collection of blood samples. Alternatively, venipuncture may be used to collect the seven blood samples.
- Blood samples will be immediately stored on ice and centrifuged within 30 minutes of collection at 1000-1300 x g (rcf) for 10 minutes at 4°C to separate the plasma.
- Immediately after centrifugation of whole blood, use a 1.0 mL pipette to transfer exactly 1.0 mL of plasma to labeled, cryovials containing 1.0 mL of plasma stabilizer (2-(N-morpholino) ethanesulfonic acid (MES)). Add a second 1.0 mL of plasma to a second cryovial to serve as a back-up sample.
- Cap the cryovials and mix the plasma with the preservative stabilizer by inverting at least six times. Freeze and store at -80 °C. No more than 60 minutes should elapse between the blood draw and freezing of plasma sample.
- An additional 8ml blood sample will be collected for imipenem and relebactam protein binding determination at 0.5 hours (end of infusion). Plasma will be separated by centrifugation as previously explained. Approximately 0.9 mL of plasma will be loaded in an ultrafiltration device (Centrifree®, Merck Millipore Ltd., Ireland) and centrifuged for 45 minutes at 10° C at 2,000 x g to obtain an ultrafiltrate containing only free-drug concentrations. Protein binding will be conducted in triplicate. The protein-free ultrafiltrate volume will be measured, transferred to a cryovial and then, an equal volume of the stabilizer will be added (confirmation of processing instructions for protein-free imipenem and relebactam will be provided by Q2 Solutions, Ithaca, NY). The cryovials will be stored at -80° C until concentration determination. The final protein percentage will be calculated by dividing the free concentration by the total plasma concentration and subtracting from 100 (%).

Study Day 2

- Clinical Assessments:
 - Perform a complete physical examination

	
 Record resting pulse, blood pressure, and respiratory rate; oxygen saturation (by pulse oximeter), including rate of supplemental oxygen (i.e., FiO₂); ventilator support; and highest (or lowest if hypothermia) daily temperature (oral, rectal, tympanic, or core) measured Identify, assess, and record any new adverse events or Serious Adverse Events (SAE) Laboratory Assessments: 
 Collect the following labs within 24 hours after completion of last blood sample collection: serum creatinine, blood urea nitrogen, glucose, sodium, potassium, chloride, bicarbonate, albumin, total protein, complete blood count (CBC) with differential, total bilirubin, direct bilirubin, alkaline phosphate, alanine aminotransferase, aspartame aminotransferase, and urine analysis with microscopy. 												
2.6 Study Duration	
 
 Final Protocol	2 months	
 
 IRB Approval	2 months	
 
 Enrollment and Sampling	10 months	
 
 Imipenem-relebactam Analytical (by Sponsor)	TBD	
 
 Pharmacokinetic Analyses	1 months	
 
 Final Report	1 months	
 
	Final Protocol	2 months	IRB Approval	2 months	Enrollment and Sampling	10 months	Imipenem-relebactam Analytical (by Sponsor)	TBD	Pharmacokinetic Analyses	1 months	Final Report	1 months
Final Protocol	2 months												
IRB Approval	2 months												
Enrollment and Sampling	10 months												
Imipenem-relebactam Analytical (by Sponsor)	TBD												
Pharmacokinetic Analyses	1 months												
Final Report	1 months												
2.7 Statistical Analysis and Sample Size Justification	
Data Analyses
 
Data Collection Patient demographics, medical/surgical history, concomitant medications, and adverse event data will be collected throughout the study on a provided case report form. Protected Health Information (PHI) will be maintained at CAIRD.
 
Analysis Populations All patients enrolled will be included in the safety population. However, only the 8 patients who meet the definition of ARC will served as the primary pharmacokinetic population. Any additional patients enrolled who do not meet the definition of ARC will have imipenem and relebactam concentrations determined for informational purposes. These patients will not be included in the summary pharmacokinetic analyses.
 
Analytical Cryovials containing plasma and protein free filtrate will be overnight shipped on dry ice to Q2 Solutions (Ithaca, NY) for imipenem and relebactam concentration determination. The back-up vial will be shipped separately. Imipenem and relebactam concentrations will be determined by a liquid chromatography mass spectrometry assay.
 
Pharmacokinetic Analyses Non-compartmental Non-compartmental modeling will be conducted using WinNonlin (Pharsight Corporation, Cary, NC) using the latest version licensed for the laboratory. All concentration time curves will be plotted for visual inspection. The following pharmacokinetic parameters will be estimated for imipenem and relebactam in each of the 8 participants. The maximum concentration (C_{max}) will be the highest concentration observed for the concentration time profile of each participant. The time to maximum concentration (T_{max}) will be the observed sampling time of the C_{max}. The minimum concentration (C_{min}) will be the lowest concentration observed for the concentration time profile of each participant that occurs after the observed C_{max}. Lambda (λ_z) will be the resulting slope of the regression line
												

of best fit. Half-life ($T_{1/2}$) will be calculated as $\ln(2)/\lambda_z$. Area under the curve for the dosing interval ($AUC_{0-\tau}$) will be calculated by the linear/log trapezoidal rule (linear during increasing concentrations, log during decreasing concentrations), where τ is the dosing interval for the drug studied. The AUC to infinity (AUC_{INF}) will be calculated as the AUC extrapolated to infinity by the equation: $AUC + C_{last}/\lambda_z$. Clearance (CL) will be estimated by $Dose/AUC_{0-\tau}$. The volume of distribution based on the terminal elimination phase (V_z) will be estimated by $Dose/(\lambda_z * AUC_{0-\tau})$.

Population Pharmacokinetic Analyses

Imipenem and relebactam concentrations will be modeled using the non-parametric adaptive grid program (NPAG) with adaptive gamma in the Pmetrics package for R (Laboratory of Applied Pharmacokinetics and Bioinformatics, Los Angeles, CA) using either a one or two compartment model. Appropriate model selection will be based on visual inspection, observed versus predicted plots, and Akaike Information Criterion (AIC). The effect of specific body size descriptors (actual body weight, ideal body weight, body mass index, body surface area) and both calculated and measured CrCL will be analyzed for correlation with pharmacokinetic parameters (i.e., CL and volume of distribution).

Monte Carlo Simulation

Using the population pharmacokinetic model, a 5000 patient Monte Carlo simulation will be conducted for the standard imipenem and relebactam dosing regimen to determine probability of achieving pharmacodynamic thresholds, as defined by Sponsor, at the imipenem susceptibility breakpoint of 2 µg/mL. Observed fraction unbound estimates from the protein-free ultrafiltrate studies in these patients will be incorporated into simulations. In the scenario that the probability of target attainment (PTA) is less than 90%, a higher dose and longer infusion time (e.g., 2-3 hours) will be simulated to determine a dose that achieves at least 90% PTA. Analyses will also be conducted using contemporary MIC distributions of *P. aeruginosa* and KPC producing *K. pneumoniae*.

Power/Sample Size:

Based upon relebactam single dose pharmacokinetic data from healthy volunteers receiving the drug with or without imipenem (3), clearance across all doses was 8.6 L/h with a standard deviation of 1.2 L/h. Eight in the ARC group would provide 80% power at an alpha of 0.05 to detect a 40% difference in total body clearance from the historical healthy volunteer data; this also assumes an increase in coefficient of variability (CV) to 25%, which is expected in critically ill patients. Since some patients with calculated CrCL via Cockcroft-Gault will not have 8 hour urine CrCL of at least 130 ml/min/1.73 m², this study will enroll up to 12 patients to have complete data for 8 patients with ARC. Enrollment will stop once complete data for 8 patients who meet the definition of ARC is confirmed or a maximum of 12 patients complete the study, whichever occurs first.

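### The serum creatinine in the measured-CrCL formula is not tied to the urine collection, so a patient near 130 mL/min whose creatinine is changing could be misclassified for ARC

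*Combined protocol and SAP*

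**What the plan says.** Section 2.5, Study Day 1, sets two windows separately. For serum creatinine (SCr): "Within 8 hours of beginning study medication infusion, a pre-dose SCr will be collected". For urine: an 8 hour (± 1 hour) "urine creatinine collection will be initiated within 4 hours prior to study medication infusion". The measured-CrCL formula that follows has the pre-dose SCr as its only serum value. Its purpose is stated there: "The results of the measured urine CrCL will be used to confirm ARC in the patient over the time period that blood samples" are taken.

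The pre-dose SCr also serves as an eligibility check. Calculated CrCL must still be at least 130 mL/min, and the plan requires that "no change in SCr was observed to be ≥ 0.3 mg/dL from the baseline SCr used qualifying for enrollment". Exclusion criterion 5 applies the same limit to any SCr before dosing.

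The next scheduled SCr is on Study Day 2: "Collect the following labs within 24 hours after completion of last blood sample collection: serum creatinine". The formula does not use it, and no SCr is scheduled after dosing while urine is still being collected.

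Section 2.2 gives the ARC definition: "This enhanced clearance is typically defined by an 8 hour urine creatinine clearance" of at least 130 mL/min/1.73 m². Section 2.7 (Analysis Populations) makes this the gate: "only the 8 patients who meet the definition of ARC will served as the primary pharmacokinetic population". Of patients who do not meet it, the plan says "These patients will not be included in the summary pharmacokinetic analyses". Section 2.7 also tests calculated and measured CrCL against clearance and volume, and stops enrolment at 8 confirmed ARC patients with complete data or 12 completed patients.

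**The concern.** A urinary clearance is the amount excreted over an interval divided by the average serum concentration over that interval. Here the numerator is measured over a defined 7 to 9 hours, but the denominator may come from hours before that period begins. If SCr is rising, an early value is too low and CrCL is overstated. If SCr is falling, CrCL is understated.

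The result is applied as a cut-off. In a primary population of 8, one patient on the wrong side is 1/8 = 12.5% of the data. The same value feeds the stopping rule, and noise in it weakens any relation between measured CrCL and drug clearance.

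**Working it through.** The plan gives no figure for this error. The check is arithmetic on its time windows and its formula.

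**1. Timing.** Inputs from section 2.5, in hours relative to infusion start: SCr draw s between -8 and 0; collection start u between -4 and 0; collection length D between 7 and 9. The midpoint is u + D/2, and the lag from draw to midpoint is u + D/2 - s.

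- Latest draw, earliest midpoint: -4 + 3.5 - 0 = -0.5 h (draw 0.5 h after the midpoint).
- Earliest draw, latest midpoint: 0 + 4.5 + 8 = 12.5 h (draw before the midpoint).
- Lag from draw to collection start, u - s: from -4 - 0 = -4 h (draw 4 h into the collection) to 0 + 8 = 8 h (draw before it begins).
- With the draw fixed at -8 h, the midpoint lag runs from 7.5 h (u = -4, D = 7) to 12.5 h (u = 0, D = 9).

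**2. Size of error.** Computed CrCL / true CrCL = mean SCr during collection / pre-dose SCr. The documents give no SCr values or drift, so the figures below are assumptions. The threshold is taken as 130 on the scale of the plan's formula.

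- Pre-dose 0.6, mean 0.7 mg/dL: ratio 1.167. A computed 150 is truly 150 × 0.6/0.7 = 128.6.
- A rise of 0.1 mg/dL from 0.6, 0.7 or 0.8 overstates CrCL by 16.7%, 14.3% or 12.5%. A rise of 0.05 overstates it by 8.3%, 7.1% or 6.3%.
- A computed value C is truly below 130 only if mean SCr exceeds the pre-dose value by more than C/130 - 1: 7.7% for 140, 15.4% for 150 and 30.8% for 170.

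**3. How fast SCr must change.** Take linear drift from a draw at -8 h. A mean of 0.7 from 0.6 needs 0.1 mg/dL in 7.5 to 12.5 h, which is 0.1 × 24/12.5 = 0.19 to 0.1 × 24/7.5 = 0.32 mg/dL per 24 h. If 0.7 is reached only at the end of collection, the rise at the midpoint is 0.1 × 8.5/13 = 0.065 (u = -4, D = 9) to 0.1 × 11.5/15 = 0.077 (u = 0, D = 7). A computed 150 is then truly 135 to 133, still ARC.

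**4. Chance of wrong ARC status.** Let computed CrCL be true CrCL times a lognormal error with log-scale SD of 5%, 10% or 15% (assumed).

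| True CrCL | 5% | 10% | 15% |
|---|---|---|---|
| 120 | 5.5% | 21% | 30% |
| 140 | 7% | 23% | 31% |
| 150 | 0.2% | 8% | 17% |
| 170 | 0% | 0.4% | 4% |

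**5. Effect of the change.** With SCr drawn inside the collection, the largest distance from the midpoint is 9/2 = 4.5 h instead of 12.5 h. Take the 12.5 h case with SCr 0.6 at the draw and 0.7 at the midpoint, a drift of 0.1/12.5 = 0.008 mg/dL per hour. SCr is 0.6 + 8 × 0.008 = 0.664 at collection start and 0.736 at its end. Computed CrCL is then 90/0.664 = 135.5 or 90/0.736 = 122.3, against a true 128.6. The error falls from 16.7% to about 5% either way. It is reduced, not removed.

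**The case against.** The windows permit the gap but do not require it. A reader might infer that the SCr always precedes the midpoint by 7.5 to 12.5 hours. That holds only for a draw at exactly -8 h, and a draw inside the collection complies equally well.

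A reader might also infer that the 0.3 mg/dL limit lets through swings of 36% to 48% (0.29/0.8 and 0.29/0.6). This ignores the second pre-dose check. A rise of 0.29 still leaves calculated CrCL at 130 only if baseline was at least 130 × 0.89/0.6 = 193, or 130 × 1.09/0.8 = 177. The exclusions for kidney disease or renal replacement, rhabdomyolysis, oliguria and refractory hypotension also select against unstable renal function. All of this stands. None of it limits change after the pre-dose draw.

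Larger examples can be built, but they need steep drift. A mean of 0.8 from 0.6 would bring a computed 150 down to 112.5. That takes 0.2 × 24/12.5 = 0.38 to 0.2 × 24/7.5 = 0.64 mg/dL per 24 h, faster than the 0.3 mg/dL that the plan treats as disqualifying.

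A reader might infer a loss of power. The stated 80% is approximately reproduced (79%) by a two-sided one-sample t test with n = 8, a difference of 0.40 × 8.6 = 3.44 L/h and SD 0.25 × 12.04 = 3.01 L/h. It would fall to 68% or 55% if one or two of the 8 had no clearance increase at all. The documents do not support that premise: a patient with a true CrCL just under 130 need not have healthy-volunteer clearance.

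The covariate analysis also includes calculated CrCL, so it does not rest on measured CrCL alone.

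**Conclusion.** The point holds as a gap in the timing rule. The serum value that decides ARC status may be drawn from 0.5 h after to 12.5 h before the midpoint of the collection, and nothing in the plan controls change after the draw. The consequence is conditional: it reaches only a patient whose CrCL is near 130 mL/min and whose SCr is changing. With stable SCr, or CrCL well above 130, it is negligible.

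A reader might infer that patients will in fact be misclassified. The documents cannot show that. They contain no drift data, so the frequency is unknown, and every magnitude above rests on assumed SCr values or drift. The stated sample size is unaffected. This is an inexpensive improvement at the gate to a very small analysis population.

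**What to change.** Keep the pre-dose SCr as the eligibility check. In section 2.5, require the SCr used in the measured-CrCL formula to be drawn between the actual start and end of the urine collection, preferably near its middle, and record the clock times of the draw and of both ends of the collection. It can be:

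- the pre-dose SCr itself, when drawn at or after the start of collection; or
- a creatinine taken with a scheduled PK draw, or a routine laboratory value, from within that interval.

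Where both a pre-dose and an in-interval value exist, report whether ARC status differs between them.

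Two simpler remedies do not work. Averaging with the Day 2 SCr brings in a value from 6 to 30 h after infusion start, up to 30.5 h from the midpoint, so patients could be reclassified on changes after the collection ended. A limit of 4 h before infusion still allows the draw to precede a collection that starts at infusion by 4 h, and its midpoint by 4 + 4.5 = 8.5 h.

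The cost is less freedom in timing the draw or, at most, one additional routine creatinine per patient in up to 12 patients. Moving the eligibility SCr itself to the 0 hour PK draw is not advised, because the result may not be back before dosing.
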